1.4 BENEFIT - RISK ASSESSMENT

1.4.1 Benefits

Anti-PD-1 checkpoint inhibitors have demonstrated efficacy in a variety of cancer types and at different stages of disease development, including as neoadjuvant treatment.

BI 765063 blocks SIRP α on the SIRP α /CD47 pathway, a receptor strongly expressed by myeloid cells, including macrophages. It restores effector functions of these cells, an activity that promotes the immune surveillance. It helps modify tumor associated macrophages (TAMs) and MDSC associated with a poor prognosis, possibly by transforming them into cells with "anti-tumor" (pro-inflammatory) properties.

As monotherapy,

[REDACTED] (modifying the phenotype and function of myeloid derived suppressor cells [MDSCs], increasing myeloid chemokine secretion and T-cell infiltration in tumor core, decreasing exhausted T-cells).

As mentioned above, neoadjuvant immunotherapy may confer protection from metastatic disease.

This trial is an opportunity to show that the benefits observed with checkpoint inhibitors and anti-SIRP α treatments in animal models will benefit CRC patients in the neoadjuvant setting. With this trial, we intend to show this by evaluating pathological response and safety of the

combinations. It is hoped that any efficacy from this treatment, [REDACTED]

1.4.2 Risks

Table 1.4.2: 1 displays the anticipated side effects of the study drugs, based on the mechanism of action, observed clinical data from ongoing studies, and published clinical data for drugs targeting SIRP α and PD-1 as well as the risk of trial procedures.

Table 1.4.2:1 Overview of trial related risks

Possible or known risks of clinical relevance for this trial	Summary of data, rationale for the risk	Mitigation strategy
Investigational Medicinal Products BI 765063 and ezabenlimab		
Unexpected adverse events and laboratory abnormalities	Due to limited clinical experience of the drugs.	Close monitoring of the data to ensure timely detection and reporting of any unexpected event. A Data Review Committee (DRC) will evaluate safety, feasibility, efficacy and biomarker results as available.
Immune-related adverse events (irAEs)	irAEs are associated with immune mediated mode of action and can be potentially severe.	Recommendations for the management of irAEs are provided according to international guidelines and product labels of approved PD-1 inhibitors [P19-00269]
Infusion related reactions (IRR)	As with any mAb, hypersensitivity reactions to study medication administration are possible and they are potentially severe.	Patients with history of severe hypersensitivity reactions to other mAbs are excluded. Recommendations for the management of infusion related reactions are given in Section 5.2.6.1.4
Drug Induced Liver Injury (DILI)	Rare but can be a potentially severe event, thus, under constant surveillance by sponsors for all drugs in development.	Timely detection, evaluation, and follow-up of laboratory alterations in selected liver laboratory parameters to ensure patients' safety.
Trial procedures		
Biopsies	Patients may experience biopsy related AEs such as pain or bleeding.	Site has to be selected based on ability and experience in performing all required trial procedures.

Possible or known risks of clinical relevance for this trial	Summary of data, rationale for the risk	Mitigation strategy
		The risks are clearly explained in the informed consent document.
Delay in surgery	Treatment related adverse events leading to delays in surgery	Patient will be monitored on an ongoing basis by the DRC for safety including treatment related events that may lead to a delay in surgery. The frequency of these events will be monitored, and enrolment will be adapted accordingly.

Potential risks related to BI 765063:

Based on its characteristic or mechanism of action, the primary safety concerns of SIRP α antagonism by BI 765063 are immune-related adverse events, infusion reactions and embryo-fetal toxicity. The 1443-0001 study is the FIH study to investigate BI 765063. Preliminary clinical safety information indicates that BI 765063 monotherapy in patients with advanced metastatic cancer is well tolerated with no reported DLTs or treatment related death.

Infusion-related reactions (IRRs) were reported by approximately half of the patients in the BI 765063 monotherapy dose escalation part of trial 1443-0001, when premedication prior to cycle 1 was not allowed. The majority of the IRRs were grade 1 to grade 2 and were well manageable. Pre-medication with an antihistamine and acetaminophen or paracetamol prior to cycle 1 resulted in a markedly reduction of IRR (as observed in the BI 765063 dose escalation in combination with fixed dose ezabenlimab part of trial 1442-0001).

Potential risks related to ezabenlimab:

Based on its mechanism of action, the primary safety concerns of PD-1 antagonism by ezabenlimab are immune-mediated adverse reactions, infusion reactions, and embryo fetal toxicity. Preliminary clinical safety information indicates that ezabenlimab monotherapy in patients with advanced metastatic cancer is well tolerated with no reported dose limiting toxicities (DLTs), treatment related SAE or treatment related deaths.

The available safety data from these patients suggests that treatment with ezabenlimab is anticipated to have a similar adverse events pattern to the currently marketed anti-PD-1 mAbs, with immune related adverse events (irAEs) as the most common AEs. These side effects are well manageable with validated guidelines.

Developmental and reproductive toxicology studies have not been conducted with ezabenlimab. Based on animal models, the PD-1/PD-L1 pathway is involved in the induction of maternal immune tolerance to allogenic fetal tissue, and therefore, is important in the maintenance of pregnancy. Administration of ezabenlimab is not expected to affect fertility

but may increase the risk of abortion and premature infant death if administered to pregnant women. Therefore, pregnant women are to be excluded from clinical trials and contraception measures as described in the informed consent have to be observed.

Potential risks related to pembrolizumab:

Potential risks related to pembrolizumab have been described. Please refer to the US Package Insert.

Potential risks related to the combination of BI 765063 and ezabenlimab / pembrolizumab:

Owing to the mechanism of action of each product and given that BI 765063 may potentiate the effect of ezabenlimab / pembrolizumab by increasing the adaptive immune effectors, special attention will be given to potential increase in irAEs in patients receiving the combination treatment.

Immune-related AE management guidance will be provided in the Section [5.2.6.1.4](#). Infusion-related reactions have been reported with checkpoint inhibitor treatment (as for all protein therapeutics). These reactions occur infrequently and are typically managed based on symptoms using treatments ranging from treatment with histamine antagonists, in mild cases, to administration of epinephrine, when symptoms of anaphylaxis are detected.

Potential risks related to COVID-19:

Based on their mode of action, the trial drugs are not expected to have a relevant impact on the susceptibility to or the course of an infection.

In case of a confirmed infection, trial treatment will not be provided and appropriate measures for monitoring, treatment and quarantine will be implemented. The patient may be treated following recovery from a SARS-CoV-2 infection if the patient is expected to derive clinical benefit, as agreed between the investigator and sponsor.

In case of an increased risk of SARS-CoV-2 infection due to the physical visits to the sites, the visits should be avoided where the investigator judges that this is the safest course of action. These measures ensure the safety of the patients throughout the trial, maintain the integrity of the trial and will not affect the benefit-risk ratio of BI 765063 given in combination with ezabenlimab or pembrolizumab.

1.4.3 Discussion

The risk-benefit relationship has been carefully considered in the planning of the trial. Based on the pre-clinical and clinical data available to date on the Investigational Medicinal Products (IMPs), the conduct of the trial is considered justifiable using the doses and dose regimens of the IMPs as specified in this CTP.

Patients will receive a single administration of trial medication (either a single dose ezabenlimab in combination with BI 765063 or a single dose pembrolizumab in combination

with BI 765063). Therefore, temporary or permanent discontinuation of trial treatment is not applicable in this trial. However, there is a remaining possibility that the administration of trial medication will be temporary or permanently discontinued during the infusion (administration) of trial medication or between the administration of the two combination drugs due to safety reasons or due to withdrawal of informed consent. It is expected that the safety risks associated with repeated exposure will not be a factor in this trial.

Respective risk mitigation measures, with regard to the expected potential adverse drug reactions to the IMPs and study procedures, have been implemented in the current clinical study. The measures taken during the trial to mitigate the risks are:

A Data Review Committee (DRC) will be established to oversee and assess the progress of the clinical trial, specifically for safety, feasibility, efficacy and biomarker results as available. Please see section [3.1](#)

- The safety of the patients will be monitored continuously. All SAEs, irAEs, and adverse events of special interest (AESI) will be closely followed and reviewed with the DRC as necessary.
- Guidance in case of irAEs have been defined in the trial protocol.
- Regular clinical and biological monitoring of patients and their data will be performed during the study period by the investigators and the sponsor.
- In order to avoid a delay in surgery, study treatment will be provided as soon as possible. The results from the biomarker assessments will not be immediately available. Study treatment will be provided as soon as possible and will not be delayed by the availability of the biomarker assessment results (e.g. genotyping).

Considering the medical need for the development of a better tolerated and more effective treatment for patients with CRC,

2. TRIAL OBJECTIVES AND ENDPOINTS

2.1 MAIN OBJECTIVES, PRIMARY AND SECONDARY ENDPOINTS

2.1.1 Main objectives

Primary objective:

The primary objective of the trial is to investigate safety and feasibility of single administration of ezabenlimab in combination with BI 765063 and single administration of pembrolizumab in combination with BI 765063 in patients with early stage resectable colorectal cancer in neoadjuvant setting.

The proportion of patients experiencing a safety and feasibility event at any time will be estimated for each arm. This is defined as a composite of whether treated patients experience one or more treatment-related events of the following types: grade 3 and higher adverse event

(according to NCI CTCAE v5.0) or treatment related adverse events leading to delays in surgery.

Secondary objectives:

- To investigate the efficacy of the study treatments.

Exploratory objectives:

- To investigate the biological activity of the study treatments.

2.1.2 Primary endpoint(s)

The primary endpoint is a composite endpoint which estimates proportion of patients with at least one occurrence of a safety or feasibility event. The detailed definitions of safety and feasibility are as follow.

Safety

Safety is defined as any grade 3 or higher adverse events (according to NCI CTCAE v5.0) related to study treatments at any point within the follow up period following the administration of study treatments.

Feasibility (delay in surgery)

Feasibility or [REDACTED]

Patient's surgery is scheduled to take [REDACTED] following the administration of study treatment. [REDACTED]

2.1.3 Secondary endpoint(s)

- **Pathologic response** (PR) defined as at least 50% or more tumor regression classified as per Mandard tumor regression grading system ([R21-1544](#)), in viable adenocarcinoma cells in the surgical specimen, including lymph nodes. Pathological response includes complete pathology response (CR), near complete pathological response (near CR) and partial pathological response ([R21-0915](#)).
- **Time from administration of trial treatment to surgery**, defined as the time in days that elapses between administration of neoadjuvant trial therapy and surgical resection.
- **Radiographic response** on pre-surgical imaging, following receipt of the neoadjuvant therapy, as per RECIST v1.1.

3. DESCRIPTION OF DESIGN AND TRIAL POPULATION

3.1 OVERALL TRIAL DESIGN

This is an open-label, two-arm, parallel group, single-center Phase 1 trial of Ezabenlimab in combination with BI 765063 (Cohort A) and Pembrolizumab in combination with BI 765063 (Cohort B) in patients with early stage resectable colorectal cancer in the neoadjuvant setting. Patients will be assigned alternatingly (sequentially one by one) to either of the cohorts and will receive one-time either of the combination treatments.

This trial is exploratory by design. Both treatment cohorts are considered exploratory. Analyses performed are intended to be descriptive, and supportive of further investigation. Pembrolizumab in combination with BI 765063 is included in the design as an exploratory treatment arm for hypothesis generation. The study is planned to treat 25 patients in each arm. For details of sample size calculation please see section [7.5](#).

An overview of the trial procedures is shown in [Figure 3.1: 1](#).

[figure not shown]

Figure 3.1: 1 Overview of trial procedures (Visits, Cohorts, Imaging and Biomarker sampling)

Patients will be enrolled (screened) in the trial once they have signed the informed consent form. In addition to the medical assessment, tumor tissue (via biopsy), blood and stool will be collected during the screening visit.

Patients who meet all eligibility criteria will be treated with one dose of ezabenlimab in combination with BI 765063 or pembrolizumab in combination with BI 765063.

After the patient completes the treatment, safety assessment will be conducted and blood and stool will be collected as indicated in the [flow chart](#).

After the end of the 90 days follow-up period, an end of study (EOS) visit will be conducted in order to perform safety assessments and to collect blood for research assessment.

For more details please refer to the [flow chart](#) and [section 6.2](#).

Table 3.1:1 Study treatments and schedules

Study Treatments				
Agent	Cohort	Dose	Route	Schedule
Ezabenlimab	Cohort A	240 mg	IV	Day 1 only
Pembrolizumab	Cohort B	200 mg	IV	Day 1 only
BI 765063	Cohort A and B	██████████	IV	Day 1 only

3.1.1 Data review committee (DRC)

A total of approximately 50 patients will be treated in this trial, i.e. approximately 25 patients in each arm. A Data Review Committee (DRC) will be established to oversee and assess the progress of the clinical trial, specifically for safety, feasibility, efficacy and biomarker results as available. The DRC will operate according to specifications defined in a separate DRC charter.

The DRC will consist of the following members:

- Principal Investigator (PI), decision maker
- BI Safety physician (pharmacovigilance officer), decision maker
- BI Clinical Program Leader (CPL), decision maker,
- BI Statistician (Stat), participates if needed
- BI Clinical Trial Leader (CTL), participates if needed

All members can be represented by a deputy.

The first scheduled DRC meeting to review data will take place after approximately 5 patients in each arm have been treated, and while recruitment continues. A second meeting of the DRC will be scheduled to review the data after approximately 15 patients have been treated in each arm. After each of these meetings the DRC will recommend to continue, to modify, or to stop the trial due to any safety concern. The DRC may meet to review data any other time if deemed necessary.

3.2 DISCUSSION OF TRIAL DESIGN, INCLUDING THE CHOICE OF CONTROL GROUP(S)

The above described trial design is appropriate for a trial with exploratory intent. In order to avoid a delay in surgery, study treatment will be provided as soon as possible. Since biomarker assessment needs time for processing, study treatment will be provided without having the results of biomarker assessment (e.g. SIRP α genotype status) available. SIRP α genotype status will be assessed retrospectively. For details please see section [7.2.5](#)

3.3 SELECTION OF TRIAL POPULATION

This trial is planned as a single center trial at Icahn School of Medicine at Mount Sinai, US. Further investigational sites may be added as appropriate. Screening for the trial will stop at the site/all sites at the same time once a sufficient number of patients have been screened. The investigator/s will be notified about screening completion and will then not be allowed to screen additional patients for this trial. Patients already in screening at the time that screening has stopped will be allowed to continue if eligible.

A log of all patients enrolled into the trial (i.e. who have signed informed consent) will be maintained in the Investigator Site File (ISF) irrespective of whether they have been treated with investigational drug or not.

If retrospectively it is found that a patient has been treated with study drug in error (e.g. did not meet all inclusion criteria or met one or more exclusion criteria), the sponsor or delegate should be contacted immediately to assess the safety of the patient.

3.3.1 Main diagnosis for trial entry

Patients with diagnosis of resectable CRC will be included. Please refer to section [8.3.1](#) (Source Documents) for the documentation requirements pertaining to the in- and exclusion criteria.

3.3.2 Inclusion criteria

Patients must satisfy all the following criteria for entry into the trial (protocol):

1. Signed and dated written informed consent in accordance with ICH-GCP and local legislation prior to admission to the trial. Ability to understand and the willingness to sign a written informed consent.
2. Male or female aged ≥ 18 years at the time of ICF signature.
3. Patients with histological diagnosis of resectable CRC, or radiographic/visual findings highly suggestive, with planned confirmatory biopsy.
4. CRC lesions must be at least 1 cm in largest diameter and amenable to endoscopic biopsy.
5. Patient must be willing and able to have endoscopic biopsy (Goal 3-6 core-needle or surgical/endoscopic biopsies, final number to be determined by the physician performing the procedure as safe) of tumor prior to initiation of therapy.

Proprietary confidential information © 2022 Boehringer Ingelheim International GmbH or one or more of its affiliated companies

6. Eastern Cooperative Oncology Group (ECOG) performance status 0-1. The exception will be patients with long term disability (such as cerebral palsy) that is unlikely to significantly affect their response to therapy.
7. Patient is determined to be a surgical candidate for resection of their tumor.
8. Adequate organ and marrow function as defined below in [Table 3.3.2:1](#).

9. Women of childbearing potential (WOCBP)¹ must be ready and able to use highly effective methods of birth control per ICH M3 (R2) that result in a low failure rate of less than 1% per year when used consistently and correctly, from signature of ICF until 6 months after administration of trial treatment. A list of contraception methods meeting these criteria is provided in the patient information. For further detail refer to Section [4.3.2.3](#).

¹ A woman is considered of childbearing potential (WOCBP), i.e. fertile, following menarche and until becoming postmenopausal unless permanently sterile.

Permanent sterilisation methods include hysterectomy, bilateral salpingectomy, and bilateral oophorectomy. Tubal ligation is NOT a method of permanent sterilisation. A postmenopausal state is defined as no menses for 12 months without an alternative medical cause.

Table 3.3.2: 1

Adequate organ and marrow function for inclusion

System	Laboratory Value
Hematologic	
Absolute neutrophil count (ANC)	$\geq 1,500 / \text{mcL}$ (1,000 / mcL for African American patients)
Platelets	$\geq 100,000 / \text{mcL}$
Hemoglobin	$\geq 10 \text{ g/dL}$
Renal*	
Serum creatinine OR Measured or calculated ^a creatinine clearance (GFR) can also be used in place of creatinine or CrCl)	$\leq 1.5 \times \text{ upper limit of normal (ULN)}$ OR $\geq 60 \text{ mL/min}$ for patient with creatinine levels $> 1.5 \times$ institutional ULN
Hepatic*	
Serum total bilirubin	$\leq 1.5 \times \text{ ULN}$ OR Direct bilirubin $\leq \text{ ULN}$ for patients with total bilirubin levels $> 1.5 \text{ ULN}$
AST and ALT	$\leq 2.5 \times \text{ ULN}$
Albumin	$\geq 2.5 \text{ mg/dL}$
Coagulation*	
International Normalized Ratio (INR) or Prothrombin Time (PT)	$\leq 1.5 \times \text{ ULN}$ unless patient is receiving anticoagulant therapy as long as PT is within therapeutic range of intended use of anticoagulants
Activated Partial Thromboplastin Time (aPTT)	$\leq 1.5 \times \text{ ULN}$ unless patient is receiving anticoagulant therapy as long as PTT is within therapeutic range of intended use of anticoagulants

^a Creatinine clearance should be calculated per institutional standard.

* If laboratory criteria are not met due to what the investigator determines to be a biologic cause (e.g. Gilbert's syndrome causing elevated bilirubin or excessive muscle mass affecting creatinine) or drug-related cause (e.g. elevating in transaminases due to HAART therapy, elevated INR due to anticoagulation) then the lab values will not be used to exclude patient from this trial. Similarly, for patients with elevated bilirubin due to biliary obstruction from tumor, this will not serve as an exclusion criterion. This determination will be made by PI.

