Renal function	Blood urea or blood urea nitrogen, and creatinine. Note: Creatinine can be assessed by any of these methods: CREE (enzymatic serum creatinine assay), CREJIDMS (IDMS standardized Jaffe), or CREJ (non-IDMS standardized Jaffe).
Coagulation	Activated partial thromboplastin time (aPTT) and prothrombin time (PT) (expressed either in seconds or as percentage) or International Normalised Ratio (INR)
Urinalysis	pH, glucose, erythrocytes, leukocytes, protein, and nitrite analysed by dipstick (semi-quantitative measurements). The result will be kept in source document, but not entered in the CRF/database and will not be reported in the CTR. Clinically relevant abnormal findings will be reported either as baseline condition (if identified at the Screening visit) or otherwise as adverse event.
Pregnancy	Beta human chorionic gonadotropin (β -HCG) pregnancy test in serum performed for women of childbearing potential at Screening. Urine or serum test performed within 72 hours before study treatment on Day 1.
For patients with history of HIV or HCV infection only:	For patients with history of HIV infection: CD4+ count, Viral load, according to local standard.

	
For patients with a history of HCV infection: HCV viral load according to local standard as needed.
 
Additional testing for infectious diseases can be added as required.
 
The result will be kept in source document, but not entered in the CRF/database and will not be reported in the CTR. Clinically relevant abnormal findings will be reported either as baseline condition (if identified at the Screening visit) or otherwise as adverse event.
 
Tests performed no more than 4 weeks prior to screening (day of blood collection) can be used and do not need to be repeated for screening.

--	---

All screening labs should be performed or repeated within 10 days prior to treatment initiation with the exception of the urine pregnancy test which should be conducted within 72 hours of initiating treatment; all other screening assessments are performed within 21 days of initiation of study treatment (Day 1).

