6.2.1 Screening and run-in period(s)

Screening Period

Patients may be consented to the clinical trial if they have imaging or other findings highly suggestive of a diagnosis of CRC. Such patients should subsequently undergo diagnostic and research biopsies in parallel, during screening, in order to avoid repeating procedures. Consented patients found to have a diagnosis other than CRC will be considered as screen-fail. Such patients will be replaced.

Following informed consent, the patient will undergo screening assessments as indicated in the [flowchart](#). The assessments must fall within the acceptable Screening visit window but do not need to be performed on the same day. Screening assessments may be repeated as long as they fall within the Screening visit window of 21 days. If more than one screening assessment is available, the latest assessment prior to the start of treatment must be used to assess eligibility.

Tumor assessments performed prior to informed consent as part of routine clinical practice will be accepted if they meet the requirements of the protocol and are performed within the Screening visit window of 21 days.

There is no mandatory order of assessments, but the biopsy must only be performed on patients who are expected to be eligible. Where applicable, the pre-treatment/baseline biopsy must be obtained prior to the dose.

If the patient meets the eligibility criteria during screening, the treatment visit should be scheduled. Any baseline conditions which are present at the Screening visit should be reported in the eCRF.

Re-screening of patients who have previously failed screening will be permitted. In this situation patients will be allocated a new patient number.

- During the screening visit, demographics information will be collected. This includes: age on the day of informed consent (in years)
- Sex (male, female in order to describe the subject's sex at birth)

Proprietary confidential information © 2022 Boehringer Ingelheim International GmbH or one or more of its affiliated companies

- Gender identity (male, female, other in order to describe how the subject self-identifies regardless of their genotypic or phenotypic sex)
- For women: of childbearing potential yes / no in order to characterize the patient population and as a basis for contraception requirements
- Pregnancy testing - serum

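### The footnote to Table 3.3.2:1 admits an anticoagulated patient above therapeutic range whom the INR/PT row would turn away, and it sets no upper limit

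*Protocol*

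**What the plan says.** Inclusion criterion 8 (Protocol 3.3.2) makes Table 3.3.2:1 part of eligibility. Three pieces of the table matter here.

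- **INR/PT row.** The limit is 1.5 times the upper limit of normal (ULN), "unless patient is receiving anticoagulant therapy as long as PT is within therapeutic range of intended use of anticoagulants".
- **aPTT row.** The same limit applies, "unless patient is receiving anticoagulant therapy as long as PTT is within therapeutic range of intended use of anticoagulants".
- **Footnote.** The asterisk sits on the Renal, Hepatic and Coagulation headings. The footnote applies when a laboratory criterion is missed for a biologic or drug-related reason. Its drug-related examples end with "elevated INR due to anticoagulation) then the lab values will not be used to exclude patient from this trial". It closes with "This determination will be made by PI".

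The footnote neither repeats the therapeutic-range condition nor gives a maximum value. I found no INR or PT ceiling elsewhere in the protocol or in the SAP.

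On timing, Protocol 6.2.1 says "There is no mandatory order of assessments", but it reserves the biopsy for patients expected to be eligible. Protocol 5.2.3 adds "All screening labs should be performed or repeated within 10 days prior to treatment initiation".

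**The concern.** The row states an upper bound for patients on anticoagulants: the top of the therapeutic range. The footnote is triggered precisely when that bound is exceeded, and it then removes the value as a reason to exclude. In-range patients already meet the row and need no waiver. So for INR raised by anticoagulation, the footnote acts only on values that are above 1.5 times ULN and also out of range.

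Every patient is to have a tumor biopsy before treatment, with a goal of three to six samples. The protocol's own risk table (Table 1.4.2:1) lists bleeding as a biopsy risk. Its stated mitigation is site experience and informed consent, not a coagulation limit. Anticoagulants are not on the prohibited list in 4.2.2, so such patients can be enrolled. What is at stake is a written entry limit that has no force for the one group it was written to bound.

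**Working it through.** The plan gives no figure to reproduce, so the check sets the row against the footnote case by case.

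**Inputs from the protocol:** the limit of 1.5 times ULN, the in-range exception in the row, and the footnote waiver. **Assumed for illustration only:** INR ULN of 1.2 and a target range of 2 to 3, so the numeric limit is 1.5 × 1.2 = 1.8. The last column applies the limiting passage set out under the fix.

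| Case | Row met? | Footnote as written | With limiting passage |
|---|---|---|---|
| 1. Anticoagulated, INR 1.5 | Yes | Not needed | Admitted |
| 2. Anticoagulated, INR 1.9 (above 1.8, below range) | No | Admits | Admitted |
| 3. Anticoagulated, INR 2.5 (in range) | Yes | Not needed | Admitted |
| 4. Anticoagulated, INR 3.5 (above range) | No | Admits | Not admitted until corrected |
| 5. Not anticoagulated, INR 1.9, no other biologic or drug-related cause | No | Does not apply | Not admitted |

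Only case 4 changes. Case 2 shows that the waiver does legitimate work: that patient is less anticoagulated than the in-range patients the row already accepts. Case 5 shows that the limit of 1.5 times ULN still binds patients who are not on anticoagulants.

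**aPTT.** The footnote names only INR. An aPTT above range is reached, if at all, through the general reference to a drug-related cause, so the point is firm for INR and arguable for aPTT.

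**What the investigator decides.** Within the footnote, the determination is about cause. In an over-anticoagulated patient the cause is plain, and once it is accepted the value drops out of the eligibility decision.

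**Scale.** The documents give no frequency. Suppose 5-10% of patients are anticoagulated and 5-20% of those are above range at screening:

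- Planned 50 patients: 50 × 0.05 × 0.05 = 0.125, up to 50 × 0.10 × 0.20 = 1.0.
- The two enrolled (SAP section 3): 2 × 0.05 × 0.05 = 0.005, up to 2 × 0.10 × 0.20 = 0.04.

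**The case against.** The best defence is that this is a rule with an exception, not a contradiction. The footnote exists to override rows, it does so for renal, hepatic and coagulation values alike, and case 2 shows that the coagulation waiver has a proper use. I accept that the text yields an answer: read literally, the footnote prevails. The criticism is what that answer does to the row's upper bound.

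The second defence is that other provisions can keep such a patient out or protect them:

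- Exclusion 4 covers patients who must continue a drug likely to interfere with safe conduct.
- Exclusion 17 expressly includes therapies and laboratory abnormalities.
- Exclusion 24 covers the patient's best interest.
- Inclusion 5 requires that the patient be able to have the biopsy, and inclusion 7 that they be a surgical candidate.
- The physician doing the biopsy decides how many samples are safe.

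These safeguards are real, and a reader who inferred that an over-anticoagulated patient must be enrolled or biopsied would be wrong. All of them rest on judgement, however, and none restores the limit that the row states.

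The third defence concerns harm, and much of it stands. Screening laboratory tests fall within 10 days before Day 1, while the synopsis places surgery 2 to 6 weeks after treatment. Standard laboratory tests are repeated within five days before surgery (6.2.2). Table 5.2.3:1 includes coagulation among the safety tests, although note 2 of the flow chart gives a shorter list without it. A reader might infer that the footnote exposes patients to bleeding at resection. The documents do not support that, because an entry INR does little to control surgical bleeding weeks later.

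The link to the biopsy is closer but incomplete. Eligibility bears on it, since 6.2.1 reserves the biopsy for patients expected to be eligible. But the order of assessments is free, so the deciding value may come after the biopsy.

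**Conclusion.** The point holds as a minor patient-safety matter. An anticoagulated patient above therapeutic range fails the INR/PT row and is then admitted by the footnote, with only discretionary checks remaining. The finding rests on the wording alone; the illustrative INR values and the percentages are assumptions that show direction and scale. On those assumptions at most about one of the 50 planned patients is affected.

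Two broader readings are not supported. The first is that the footnote removes the coagulation limit for everyone, or that the whole waiver is unsound: patients not on anticoagulants keep the limit, and admitting those below range is reasonable. The second is that the results are affected: nothing in the primary endpoint, the sample size or the Bayesian boundaries depends on this text. I make no criticism of the renal or hepatic rows. The trial stopped after two patients, so the practical value lies in recording the defect and correcting it wherever the table is reused.

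**What to change.** Leave the examples in the footnote as they are. Narrowing the INR example alone would not work, because an above-range INR would still fall under the general drug-related cause. Add instead:

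*This waiver does not apply to a patient on an anticoagulant monitored by PT/INR or aPTT whose monitored value is above the therapeutic range for its intended use; such a patient may be retested after correction within the screening window. For anticoagulants without a defined PT/INR or aPTT target, eligibility is at PI discretion.*

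Tying the limit to the monitored value avoids a loophole in which a normal aPTT would excuse a high INR, and the second sentence covers agents for which a therapeutic range is undefined.

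**Cost.** Two sentences in one footnote, and a correction and retest for a very few patients. Section 6.2.1 already provides for this: "Screening assessments may be repeated as long as they fall within the Screening visit window of 21 days", and "the latest assessment prior to the start of treatment must be used to assess eligibility". Because laboratory tests must also fall within 10 days before treatment, a slow correction could push Day 1 back by some days, against the aim in section 3.2 of treating promptly so that surgery is not delayed. The change restores a stated entry limit; it does not guarantee a safe biopsy.
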